6.2.4. Electronic Diary

Subjects will be required to complete a reactogenicity eDiary through an application installed on the subject's own personal device. Site will train the subject on the application during Visit 01. All subjects will be asked to monitor and record local reactions, systemic events including temperature, and antipyretic medication usage for 7 days following administration of IP. The reactogenicity eDiary allows recording of these assessments only within a fixed time window, thus providing the accurate representation of the subject's experience at that time. Data on local reactions and systemic events reported in the reactogenicity eDiary will be transferred electronically to a third-party vendor, where they will be available for review by Investigators via an internet-based portal or reports extracted from the portal.

At specified intervals, these data will be retrieved electronically to the Sponsor for analysis and reporting. These data will be reported in the database but do not need to be reported separately by the Investigator in the eCRF as AEs.

Investigators (or designee) will be required to review the reactogenicity eDiary data daily as part of the ongoing safety review. The site will be notified if a subject has missed a diary entry. The eDiary application will remind the subject to populate the diary and will notify the site of the event. If a subject continues to be delinquent the site will contact the subject by phone and will document any missed entries as a protocol deviation. The site will also be notified if a subject has entered a Grade 3 or Grade 4 severity for a symptom. The site must contact the subject to confirm the scoring and determine whether subject should attend the clinic for further follow-up. The Investigator is required to evaluate the symptoms and assess whether they agree with the grading of 3 or higher. Regardless of the PI assessment, the diary entry will not be changed, and the Investigator will verify the score or note a discrepancy in the source.

The Investigator or designee must obtain stop dates from the subject for any ongoing local reactions, systemic events, or use of antipyretic medication on the last day that the reactogenicity eDiary was completed. The stop dates should be documented in the source documents and the information entered in the eCRF.

6.2.4.1. Local Reactions

During the reactogenicity reporting period, subjects will be asked to assess nasal congestion and rhinorrhea after IP administration. All symptoms post-IP will be recorded by the subject in the reactogenicity eDiary. If a local reaction persists beyond the end of the reactogenicity period following vaccine administration, the subject will be requested to report that information. The Investigator will enter this additional information as an AE in the eCRF.

Symptoms emerging after IP treatment will be categorized during analysis as mild, moderate, severe, or potentially life-threatening based on the grading scale in Appendix 2.

If a Grade 3 or Grade 4 local reaction is reported in the reactogenicity eDiary after IP administration, a telephone contact should occur to ascertain further details and determine whether a site visit is clinically indicated.

If a Grade 3 or Grade 4 local reaction (pain, redness, swelling at injection site) is reported after QIV administration at Visit 04 and prior to Visit 05 the site should ascertain whether a site visit is clinically indicated. Grading will be assessed according to FDA Guidance for Industry Toxicity Grading Scale for Healthy Adult and Adolescent Volunteers Enrolled in Preventive Vaccine Clinical Trials.

Only an Investigator or medically qualified person is able to classify a subject's local reaction to a QIV administration as Grade 4 and must provide a written record of the event. If a participant experiences a confirmed Grade 4 local reaction, the Investigator must immediately notify the Sponsor.

Solicited local reactions following the IP dose include:

- Runny nose
- Stuffy nose/ nasal congestion

6.2.4.2. Systemic Events

During the reactogenicity reporting periods, subjects will be asked to assess headache, fatigue, myalgia, and illness. For the post-IP period, this will include recording the symptoms in the reactogenicity eDiary. The symptoms will be assessed by the subject as none, mild, moderate, severe or medically attended – emergency room visit or hospitalization was required according to the grading scale in Appendix 1.

If a Grade 3 or Grade 4 systemic event is reported in the reactogenicity eDiary after administration of IP, a telephone contact should occur to ascertain further details and determine whether a site visit is clinically indicated. If a systemic reaction persists beyond the end of the reactogenicity period following vaccine administration, the subject will be requested to report that information. The Investigator will enter this additional information as an AE in the eCRF. If a Grade 3 systemic reaction is reported after QIV administration (Visit 04) and prior to Visit 05, the site should ascertain whether a site visit is clinically indicated. If a Grade 3 or Grade 4 respiratory event (for example cough or wheezing) has been confirmed by the site, the subject should attend the clinic to provide a nasal swab that is tested as soon as possible for the full panel of respiratory agents.

Only an Investigator or medically qualified person is able to classify a subject's systemic event as Grade 4. If a participant experiences a confirmed Grade 4 systemic event, the Investigator must immediately notify the Sponsor.

Solicited systemic events following the IP dose include:

- Fever
- Chills
- Muscle aches
- Decreased activity
- Decreased appetite
- Headache
- Cough
- Sore throat

6.2.4.3. Fever

In order to record information on fever, a digital thermometer will be provided to subjects with instructions on how to measure oral temperature at home. Temperature will be collected in the reactogenicity eDiary in the evening daily during the reactogenicity eDiary reporting period. It will also be collected at any time during the reactogenicity periods, whether during eDiary data collection (post-IP) or post-QIV interval, when fever is suspected. Fever is defined as an oral temperature of ≥38.0°C (100.4°F). The highest temperature for each day will be recorded in the reactogenicity eDiary. Temperature will be measured and recorded to 1 decimal place and then categorized during PI analysis according to the scale shown in Appendix 1.

If a fever of $\geq 39.0^{\circ}$ C (102.1°F) is reported in the reactogenicity eDiary, a telephone contact should occur to ascertain further details and determine whether a site visit is clinically indicated. Subjects should be instructed that if they record a fever of $\geq 39.0^{\circ}$ C post-administration of QIV, they should contact the site as soon as possible. Only an Investigator or medically qualified person is able to confirm a participant's fever as $\geq 40.0^{\circ}$ C ($\geq 104.0^{\circ}$ F). If a participant experiences a confirmed fever $\geq 40.0^{\circ}$ C ($\geq 104.0^{\circ}$ F), the Investigator must immediately notify the Sponsor.

6.2.4.4. Antipyretic Medication

The use of antipyretic medication to treat symptoms associated with IP administration will be recorded in the reactogenicity eDiary daily and recorded in the concomitant medications section of the eCRF during the IP reporting period (Day 1 to Day 7).

6.2.5. Immune Response Evaluations

6.2.5.1. Nasal Swabs

Nasal swabs will be collected from subjects to determine mucosal immunity.

Nasal swabs will be collected at the time points specified in the Schedules of Events (Table 2 and Table 3) from all subjects. Individual swabs will be collected from each nostril and placed

in separate vials. Samples will be shipped out for processing then aliquoted for use in various tests.

To evaluate mucosal immunity, an ELISA-based test will be used to measure mucosal IgA antibody titer to HA and total IgA concentration.

6.2.5.2. Blood Collection for Influenza Antibody Testing

Blood samples will be collected and used for serum antibody titers against influenza using MN and research assays. Samples will be collected as indicated in the Schedules of Events (Table 2 and Table 3).

The MN assay will measure all serum antibodies that neutralize the virus and prevent infection of cells and will be analyzed as directed in assay-specific protocols.

Research testing will be performed by the Sponsor or a vendor under supervision of the Sponsor. The research assays include ELISAs or similar methods that may be used to detect anti-influenza immunoglobulin G (IgG) and/or IgA antibodies against influenza HA, HA stalk or NA. Additional assays may be conducted for detection of antibody response to influenza or other respiratory virus, for example NAI assays.

Further details regarding sample collection, processing and shipping can be found in the Laboratory Manual.

6.2.5.3. PBMCs for Cell-mediated Immunity Testing

Blood samples will be collected from all subjects and peripheral blood mononuclear cells (PBMCs) will be isolated and cryopreserved to be tested for cell-mediated immunity (CMI). Samples are taken as indicated in the Schedules of Events – IP Administration (Table 2).

PBMCs will be used to evaluate T cell responses by ELISPOT assays measuring cytokine secretion upon stimulation with influenza specific peptides. PBMCs may also be evaluated using flow cytometric methods and intracellular cytokine staining to characterize the duration of the responses, and whether memory phenotypes are generated. PBMCs may also be used in a direct ex-vivo ELISPOT assay for evaluation of plasma B cell responses or for detection of memory B cell responses after stimulation.

Further details regarding sample collection, processing and shipping can be found in the Laboratory Manual. PBMC preparation will be the responsibility of each site.

7. STUDY TERMINATION/COMPLETION

7.1. Study Completion and End of Study Definition

A subject will be considered to have completed the study if he or she received the last study vaccination and attended the last protocol-defined follow-up visit.

End of study will be defined as the point when all subjects have completed Visit 05 (28 days after QIV administration). The Sponsor will notify all applicable regulatory agencies in accordance with local requirements when the study has ended.

7.2. Termination of the Study by the Sponsor

This study may be discontinued at any time due to safety concerns, failure to meet expected enrollment goals, administrative reasons, or at the discretion of the Sponsor. Should the study be terminated prematurely, the Sponsor will provide written notification to all Investigators and regulatory authorities and will specify the reason(s) for early termination. The Lead PI must inform the IRB promptly and provide the reason(s) for the termination.

7.3. Halting Rules

Vaccination of subjects with the Study IP will be suspended until after blinded review of safety data by the SRC if any of the following halting rules are met:

- 1. One or more subjects experience a Grade 4 AE assessed as related to IP.
- 2. Three or more subjects within an age group experience the same Grade 3 AE assessed as related to IP.
- 3. One or more subjects experiences an SAE assessed as related to IP.
- 4. One or more subjects has laryngospasm, bronchospasm, or anaphylaxis associated with the study IP within 72 hours after administration assessed as related to IP.

Any AE or SAE that falls into the above criteria for suspending or terminating study vaccinations must be reported by the Investigator to the Sponsor immediately (within 24 hours).

In the case of AEs meeting the above criteria, the SRC will be convened as quickly as possible, but no later than 3 days after the notification of the event(s). After review of the safety data the SRC will make a recommendation to the Sponsor whether to resume, suspend, or terminate the study. The Sponsor will communicate a decision to suspend or terminate the study to the Investigators. Upon request, the SRC may be provided with an unblinded data set for review.

Subsequent review of serious, unexpected, and related AEs by the Medical Monitor, SRC, IRB, the Sponsor(s), or the Regulatory Agency may also result in suspension of further trial interventions/administration of study product at a site. The FDA and study Sponsor(s) retain the authority to suspend additional enrollment and study interventions/administration of study product for the entire study, as applicable.

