6.2.3. Adverse Events

Adverse events will be monitored regularly from informed consent until Visit 05 (28 days after QIV administration). At regular intervals during the study, subjects will be asked non-leading questions to determine the occurrence of any AEs. All AEs reported spontaneously during the study will be recorded as well. Solicited and unsolicited signs and symptoms will be reported as AEs after review by the Investigator or designee, either separately using the corresponding Medical Dictionary for Regulatory Activities (MedDRA) terminology of the sign or symptom or combined using the appropriate term. For example, a subject who reported concurrent cough, runny nose, and sneezing assessed by the Investigator as unrelated to vaccine should have those symptoms grouped as a syndromic diagnosis (URI), with the severity based on the most severe AE/symptom. Therefore, as a secondary presentation, subjects with 3 or more concurrent unrelated AEs of cough, runny nose/rhinorrhea, sneezing, sore throat, itchy throat, itchy eyes, congestion, nasal irritation, hoarseness, headache, body aches/myalgia, tiredness/fatigue, malaise, and fever will have those AEs grouped as URI.

For detailed definitions and reporting procedures of AEs, see Section 9.

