9.3. Causality Assessment

The clinician's assessment of an AE's relationship to test article (vaccine or placebo) is part of the documentation process, but it is not a factor in determining what is or is not reported in the study. If there is any doubt as to whether a clinical observation is an AE, the event should be reported. All AEs must have their relationship to study product assessed using the terms related or not related. In a clinical trial, the study product must always be suspect. To help assess, the following guidelines are used.

Related – There is a reasonable possibility that the study product caused the AE. Reasonable possibility means that there is evidence to suggest a causal relationship between the study product and the AE.

Not Related – The AE is not related to the study product if there is evidence that clearly indicates an alternative explanation. If the subject has not received the study product, the timing of the exposure to the study product and the onset of the AE are not reasonably related in time, or other facts, evidence or arguments exist that strongly suggest an alternative explanation, then the AE is not related.

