9.9. Medical Monitor

The Medical Monitor is an independent clinician (i.e., not directly employed by the Sponsor or the site) responsible for safety oversight of the study. He/she should have no apparent conflict of interest and cannot be under the supervision of the PI or other Investigators or research staff. The Medical Monitor will oversee interventions, interactions, data matching, data collection and data analysis, review the clinical monitoring plan, review SAE and SUSAR reports (Section 9.6), review AEs which may prompt a study halt (Section 7.3), participate in the SRC (Section 9.10), participate in decisions regarding emergency unblinding (Section 5.6), participate in review of Grade 3 and Grade 4 laboratory abnormalities, and review summary AE data prior to final database lock. The Medical Monitor is responsible to promptly report his/her observations to the IRB or other designated official. The Medical Monitor has the authority to stop the study, remove individual human subjects from a research protocol if needed and take any steps necessary to protect the safety and well-being of the subjects until the IRB can assess the monitor's report. The Medical Monitor will also participate via phone in site training and will be available to answer questions related to study eligibility and safety for the duration of the study and may discuss the research protocol with Investigators.

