9.2. Adverse Events (AEs)

Adverse events were to be recorded from the day of informed consent through QIV Day 29. For subjects without QIV administration, follow-up for both AEs and SAEs was 28 days after IP. During the study treatment period subjectswere asked non-leading questions to determine the occurrence of spontaneously reported (unsolicited) AEs.

Symptoms were collected for the 7 days following IP administration using eDiaries, with clinical interpretation of data entries by the site investigator. At the discretion of the investigator, a symptom recorded by the subject on the eDiary may have been reported as an AE. The investigator was responsible for determining the severity and the relationship to IP for any eDiary-based AEs. There was no reconciliation of the database between the eDiary symptoms and other AE reports.

PE findings recorded as clinically significant, severe, or life threatening were to be recorded as AEs. Investigators usedtheir judgement regarding reporting of additional PE findings as AEs.

All AEs will be included in the listings. Only treatment emergent AEs will be summarized.

Separate listings of subjects who died, discontinued the study due to an AE, or experienced an SAE will be provided.

Treatment-emergent AEs (TEAE) are AEs with start dates between administration of the IP and IP Day29. If there is no administration of QIV then AE/SAE follow-up will be 28 days post IP administration. However, AEs with start dates past Day 29, if judged by the investigator to be IP-related, will be included in the treatment emergent set.

All AEs will be coded based on MedDRA (V24.0).

Where provided in Protocol Appendix 1, AEs will be graded according to the Vital Sign and Systemic Toxicity Assessments.

N (%) of subjects with at least one TEAE and N (%) of subjects with at least one treatment-related treatment-emergent AE (TRAE) will be summarized. TEAE and TRAE by worst severity will be summarized.

N (%) of subjects with TEAE will be reported by System Organ Class and Preferred Term (SOC/PT) and maximum severity. N (%) of subjects with TRAE will be reported by SOC/PT and maximum severity.

N (%) of subjects with TEAE by SOC/PT by overall frequency (decreasing) will be reported.N (%) of subjects with TRAE will be reported by SOC/PT by overall frequency (decreasing).

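### A confirmed Grade 3 diary reaction may never get the relatedness call that halting rule 2 needs, and the 24-hour duty in Protocol 7.3 is unclear for the first two events of a count that runs across sites

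*Protocol*

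**What the plan says.** **The rule.** Protocol 7.3, rule 2, suspends IP dosing if "Three or more subjects within an age group experience the same Grade 3 AE assessed as related to IP". The count is by age group and has no site limit. The reporting duty follows: "Any AE or SAE that falls into the above criteria for suspending or terminating study vaccinations must be reported by the Investigator", to the Sponsor, within 24 hours. The Safety Review Committee (SRC) must then meet within 3 days of notification.

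**How a diary symptom becomes an AE.** The sections differ.

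- Protocol 6.2.3: "Solicited and unsolicited signs and symptoms will be reported as AEs after review by the Investigator or designee".
- Protocol 6.2.4, on diary data: "These data will be reported in the database but do not need to be reported separately by the Investigator in the eCRF as AEs".
- Protocol 6.2.4.1 and 6.2.4.2: the Investigator enters a local or systemic reaction as an AE if it outlasts the diary period.
- Protocol 9.3: "All AEs must have their relationship to study product assessed using the terms related or not related".
- Protocol 9.5: every AE goes into the source documents and the eCRF.
- SAP 9.2: "At the discretion of the investigator, a symptom recorded by the subject on the eDiary may have been reported as an AE". It adds that diary symptoms and AE reports were not reconciled, and that the investigator judged severity and relationship for diary-based AEs.

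**Oversight.** Under Protocol 3.1 the Medical Monitor and lead PI review blinded safety data before Cohorts 2 and 3 open. The SRC has two informational meetings, on data after Cohorts 1 and 2. SAP 8.5 lists no further planned review. Protocol 9.9 gives the Medical Monitor the task of reviewing AEs that might lead to a halt, and the authority to stop the study.

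**The concern.** Rule 2 works on AEs that carry a relatedness assessment. Solicited reactions in the week after dosing are the events most likely to feed it. A site that follows 6.2.4 as written can confirm a Grade 3 headache or nasal congestion, telephone the subject, note the grade in the source, and enter no AE. If the symptom resolves within the diary week, the persistence clause does not apply either. Nothing else then requires a relatedness call, and without one the event cannot count toward three.

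The second issue is timing. Rules 1, 3 and 4 trigger on one subject, so a single Investigator knows when to report. Rule 2 alone needs pooling. An Investigator with one related Grade 3 event cannot tell whether it is the first or the third in the age group. If that event need not be sent promptly, recognition of the third waits on routine data flow. The SRC's 3 days start only at notification, and dosing can continue meanwhile. This is the vaccine's first use in older adults, and 90 of the 120 subjects are in Cohort 3, after the last scheduled review.

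**Working it through.** **1. The plan's own figure.** Protocol 1.4 gives more than a 95% chance of seeing an AE of 20% prevalence among 15 subjects. 1 − 0.8^15 = 0.965, so it reproduces. It concerns seeing at least one event and says nothing about rule 2.

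**2. Does another deadline cover a Grade 3 event?**

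| Event | Notice to the Sponsor | Section |
|---|---|---|
| Grade 3 or higher laboratory value | 24 hours | Protocol 6.2.2 (SAP 9.3: no safety labs scheduled after IP) |
| SAE | 24 hours | Protocol 9.6 |
| Confirmed Grade 4 reaction | Immediate | Protocol 6.2.4.1, 6.2.4.2, Appendix 2 |
| Withdrawal for other reasons | 2 days | Protocol 7.4 |
| Grade 3 diary event | None stated; the site contacts the subject (within 18 hours for local reactions) | Protocol 6.2.4 to 6.2.4.2, Appendix 2 |

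A non-serious Grade 3 clinical or solicited event in a continuing subject falls outside every stated limit unless 7.3 is read to include it.

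**3. How often rule 2 would be reached.** The 65–85 group is Cohorts 2 and 3: 70 vaccine, 35 placebo. Both arms count, because relatedness is judged blind. The documents give no Grade 3 rate, so the rates below are assumptions for one event term. P(X + Y ≥ 3), with X ~ Bin(70, p_v) and Y ~ Bin(35, p_p):

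| p_v | p_p = 0 | p_p = 1% |
|---|---|---|
| 1% | 0.033 | 0.089 |
| 2% | 0.165 | 0.255 |
| 5% | 0.686 | 0.746 |

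Protocol 1.3 describes related AEs in earlier adult studies as generally mild or moderate, so the 1% row fits best.

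**4. Effect of unrecorded diary events.** Assume that only half of related Grade 3 symptoms become AEs (illustration, p_p = 0). The effective rate halves. For a true 2% rate the chance of reaching three falls from 0.165 to 0.033. For 5% it falls from 0.686 to 0.255 (Bin(70, 0.025)).

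**5. Cost of a day's delay.** Cohort 3 gets QIV 28 to 42 days after IP (Protocol 1.4), with QIV from September to early November 2021 (Protocol 3.1). The longest possible IP window runs from QIV start − 42 days to QIV end − 28 days. Exact dates are assumed.

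- QIV 1 September to 7 November: IP 21 July to 10 October, 82 days; 90/82 = 1.10 subjects per day.
- QIV 30 September to 1 November: IP 19 August to 4 October, 47 days; 90/47 = 1.91 per day.

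These are average paces over the longest windows, so actual dosing could be more concentrated. Two thirds of these subjects get vaccine. In the 1% row the expected number per trial, for each day of delay, is 0.033 × 1.10 = 0.04 to 0.089 × 1.91 = 0.17, if a delay always occurs when the threshold is reached.

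**6. Would the events be at different sites?** SAP 1.1.2.1 says randomization was local to each site, but the number of sites is not given. With s equal sites, three events fall at more than one site with probability 1 − 1/s²: 0.75 for 2 sites, 0.96 for 5.

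**The case against.** The 24-hour duty is phrased for a single AE. Since no site can know the pooled count, the reading that makes it workable is that each related Grade 3 AE is reported. Protocol 9.9 fits this, since the Medical Monitor looks at AEs that might prompt a halt, not only those that have. That reading is reasonable and may be what was meant. The next sentence of 7.3, which convenes the SRC for AEs that meet the criteria, fits the narrower reading equally well. A stopping rule should not leave sites to choose.

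On 6.2.4, the word 'separately' could mean only that double entry is avoided; Protocol 8.3 does treat diary symptoms as solicited AEs. But the clauses in 6.2.4.1 and 6.2.4.2 that call for AE entry when a reaction persists would be needless if every diary reaction were already to be entered. SAP 9.2 is retrospective, and so weaker evidence of how the halting rule was meant to run, but it shows that entry was treated as optional.

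Central data also exist. Diary entries go to one vendor portal and are retrieved by the Sponsor at intervals (6.2.4), and AEs and relatedness go into EDC (9.5). The Medical Monitor can stop the study, and the SRC can be convened on request (9.10). These are real brakes, so what remains on timing is the absence of a stated deadline. The SRC Charter and Clinical Monitoring Plan are not available and may supply one.

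A reader might infer that each site would hold back reports until it had three events of its own. The documents do not say that. A reader might also treat everyone still undosed when the third case is dosed as the harm. That number is the most an instant halt could spare; the wording costs only the days of delay.

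**Conclusion.** The point holds as a low-severity, cheap improvement. The firmer part is the AE conflict: 6.2.4, its persistence clauses and SAP 9.2 together let a confirmed Grade 3 solicited reaction go without a relatedness call, against 6.2.3, so it may be missing from rule 2's count. The weaker part is the 24-hour duty, which is ambiguous for sub-threshold events but can fairly be read to cover them.

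If the threshold is reached in Cohort 3, each day of delay exposes about 1 to 2 more subjects on average. At an assumed 1% rate on vaccine and 0 to 1% on placebo, that arises in about 3 to 9% of trials. The result rests on assumed event rates and QIV dates. Higher rates make the threshold far more likely to be reached, but the documents give no reason to expect them. Confidence is medium, because the unseen charter or monitoring plan may already set a route. The documents do not support a claim that rule 2 cannot work or that safety oversight is absent.

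**What to change.** - **Protocol 6.2.4 and 7.3:** state that every Investigator-confirmed Grade 3 or higher solicited or clinical event after IP, diary events included, is recorded as an AE with a relatedness call.
- **Protocol 7.3:** state that each related Grade 3 event goes to the Sponsor and Medical Monitor within 24 hours, the limit already used for Grade 3 laboratory values.
- **Protocol 9.9:** state that the Medical Monitor keeps the count by event term and age group across sites.

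The threshold of three does not change. The cost is protocol wording plus a few extra AE entries and expedited reports, using the existing eDiary alerts and Medical Monitor. If the SRC Charter or monitoring plan already sets the reporting route, a cross-reference covers the second and third items; the first still needs the protocol text changed.
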